5.6 By Visit

Informed consent

Informed consent will be obtained voluntarily by each subject before any study specific procedures are initiated. Patients will be given information about inclusion in the study at the out-patient clinic at Rikshospitalet, Oslo University Hospital.

The following tests will be done at screening:

Clinical status

A medical history will be recorded, including disease history and corresponding treatment details, physical examination e.g. cor/pulm/abdomen and peripheral lymph node status), vital signs (weight, blood pressure, temperature and pulse) and ECOG performance status.

Tumor evaluation: CT thorax/abdomen (pelvis) and MRI-liver within 4 weeks of MDT-meeting at Rikshospitalet. All patients included in the study will receive systemic chemotherapy as standard of care. This treatment will be given at local hospitals and as standard of care blood chemistry will be performed before administration of chemotherapy. Patients randomized to HAI will in addition have blood chemistry the day the pump is filled for a new 14-day treatment. The safety measures for the systemic chemotherapy will be standard of care and documented in the patient records according to standard procedures at the different hospitals. CT (MRI)-scans will be performed at local hospital and the CT (MRI) scans showing stable disease or response will be submitted to the HPB-meeting at Rikshospitalet for evaluation of resectability. Resectable patients (from both the control and HAI groups) will have liver resection at Rikshospitalet.

Laboratory analysis

Blood samples will be taken to determine CRP, Hb, HCT, WBC (incl.differential counting), PLT, Na, K, Ca, creatinine, ASAT, ALAT, LD, ALP, γ GT, INR, albumin, bilirubin CEA and CA 19-9. Pregnancy test will be secured within the last 14 days in fertile women.

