5.5 Schedule of events

- Identification
 - Patients are identified from referrals or during MDT-meetings by surgeon or oncologist.
 - A trial specific MDT evaluation of liver metastases and resectability is performed.
 - Following this MDT-meeting, the patient is invited for out-patient visit within 10 days.
 - If no updated high-quality thoracic/abdominal CT and MR scan is available (No older than 4 weeks by date of out-patient visit), these are booked.
- At out patient clinic:
 - Eligibility for *Excalibur* 1 or 2 is assessed.
 - In house review of new images if applicable.
 - Eligible patients receive written and oral information about the trial and risks pertaining to HAI-catheter insertion/transplant/systemic chemotherapy
 - Measurement of CEA and standard blood chemistry
 - If patient consents:
 - Baseline QoL survey (C30) and EQ5D questionnaire is completed
 - Patient's latest CT or MRI scans are referred to next MDT meeting for designation of three target lesions for RECIST evaluation
 - Availability of mutation status is confirmed. If mutation status is not already performed, this is ordered from pathology lab.
 - Decision of eligibility for *Excalibur* 1 or 2 is decided by two trial investigators. If a patient is found to be eligibility for *Excalibur* 1 a member of transplant team will concur and provide specific information about transplants.
 - If a patient has begun or is planned for 2nd line chemotherapy, the randomization MUST take place before any evaluation of 2nd line treatment effect, i.e imaging (CT/MR). (PET for evaluation of extra hepatic disease is allowed). The choice of drugs for 2nd line chemotherapy must be decided on prior to randomization.
 - Inclusion is confirmed
 - Patient card
 - The following appointments are booked within two weeks:
 - A PET scan following 4 week chemo abstinence. If the patient has recently received systemic chemotherapy, a 4 week chemo abstinence must be ensured and randomization may need to be somewhat delayed.
 - Patients eligible for *Excalibur* 1 for individual assessment by transplant team
 - An operation theatre for insertion of HAI-pump catheter at four weeks from inclusion
- PI meeting two weeks following inclusion:
 - Documents, inclusion details, transplant assessment and PET results are reviewed

- If satisfactory, a web-based randomization is performed.
- All patients:

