 - Monthly pregnancy testing should be performed in women of childbearing potential (WOCBP) as long as they receive chemotherapy according to study protocol. This can be done with a urine test at home combined with contact with the study team by phone
 - A calendar for oncologist visits and provision of systemic chemotherapy is created by coordinating nurse. Control scans are ordered for each 2nd month for the first year following randomization and as long as the patients receive chemotherapy, each 3rd month for the second year and each 6th month for the third year. MDT meetings are scheduled for one week following each new scanning to assess response and possible resectability
 - Out-patient control appointments are scheduled for outcome assessment including QoL-scoring (3, 6, 9, 15, 18, 21 and 24 months)
- Patients in HAI group (group 2 a and 2b)
 - A calendar of reservoir refills is created and harmonized with provision of systemic treatment.
 - A laparotomy is performed within 2 weeks from randomization with insertion of catheter and reservoir for HAI-pump.
- Patients in transplant group
 - Oncologists are instructed to avoid Avastin in systemic chemotherapy while the patient is listed.

Table 3: Overview of screening procedures, End of study/Withdrawal

Overview of screening procedures, End of study Withdrawal												
Item	ICF	Inc/Ex	Med Hist	Prior Trea	Phys Exam	Vit Sign	ECOG	CT/ MR	QoL	Blood Sample	Adverse Event	Survival Assessment
Screening	x	x	x	x	x	x	x	x	x	x	x	
EOS/Withdrawal											x	x

Table 4: Calendar of cycles and events for patients in HAI group

Calendar of cycles and events for patients in HAI group								
Day cycle 1 + 2	1	2	15	16	29	30	44	
Day cycle 3 + 4	61	62	75	76	89	90	104	
Pump refill FUDR at OUS	x				x			
Pump refill HepNaCl at OUS			x					x
Systemic chemo local hospital		x		x		x		

Table 5: Calendar of cycles and events for patients in control group and on waiting list for LTx-group

Calendar of cycles and events for patients in control group and on waiting list for LTx- group							
Day cycle 1 + 2	1		15		29		44
Day cycle 3 + 4	61		75		89		104
Systemic chemo local hospital	x		x		x		x

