5.6.1 Before Treatment Starts

Eligible and consenting patients will be randomized. Patients randomized to systemic chemotherapy will receive chemotherapy at their local hospital. Patients randomized to HIA and systemic chemotherapy will have the pump placement and HAI administration at the department of gastrointestinal surgery/HPB section at OUH/Rikshospitalet. The systemic chemotherapy will be administered at local hospitals. The patients in these two groups will repeatedly be evaluated for liver resection at the MDT-meeting at Rikshospitalet and patients who become resectable will have liver resection/local ablation at Rikshospitalet. Patients randomized to liver transplantation will be evaluated for liver transplantation and receive liver transplantation according to standard procedure at the department of Transplantation Medicine, Rikshospitalet. These patients will receive chemotherapy at their local hospital until time of receiving a liver transplant.

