5.6.3 Progressive disease or toxicity

In the case of progressive disease (PD) in the systemic chemotherapy arm, this treatment will be halted and shifted to 3rd chemotherapy as appropriate or to best supportive care (BSC). In the case of PD in the HAI-group, systemic chemotherapy will be changed to 3rd line as appropriate and the use of pump is discontinued. In the case of PD in the transplant group, listing is upheld but chemotherapy is changed to 3rd line as appropriate until available organ is available. In the case of toxicity a change in systemic chemotherapy to 3rd line is attempted and if unaltered toxicity, halted.

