5.10 Assessment of Efficacy

Overall survival, liver resection rates and surgical complications will be recorded from patient medical records.

Assessment of tumor response (prior to resection or transplant): tumor response will be assessed according to RECIST version 1.1, based on CT scans of thorax, abdomen and pelvis. This procedure cannot be blinded as the HAI catheter will show on all CT series.

Chemotherapy related toxicity will be evaluated using NCI-CTC v. 5.0, grade 3-5 related to systemic chemotherapy will be assessed.

Surgical complication will be assessed by Accordion grading system, only grade 3-6 will be recorded.

Quality of life will be assessed by EORTC QLQC30 and EQ5D.

Biomedical marker related to clinical outcome will be developed based on blood samples and liver biopsies collected

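### Sections 5.5 and 5.6 disagree on which on-study scans reach the central meeting; if section 5.6 is followed, a progression call is not read centrally

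*Protocol*

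**What the plan says.** Two rules govern where on-study scans go.

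- Protocol section 5.5, under the items for all patients: "MDT meetings are scheduled for one week following each new scanning to assess response and possible resectability". The result of the scan plays no part.
- Protocol section 5.6: "CT (MRI)-scans will be performed at local hospital", and "scans showing stable disease or response will be submitted to the HPB-meeting at Rikshospitalet for evaluation of resectability". Here the result decides whether the scan is sent.

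Three other places bear on the point. At baseline, section 5.5 gives the choice of lesions to the MDT: "Patient's latest CT or MRI scans are referred to next MDT meeting for designation of three target lesions for RECIST evaluation". Section 5.10 sets RECIST 1.1 for tumour response, names no reader, and says of the assessment: "This procedure cannot be blinded as the HAI catheter will show on all CT series". Section 5.6.1 says of the control and HAI groups: "The patients in these two groups will repeatedly be evaluated for liver resection at the MDT-meeting at Rikshospitalet".

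A progression call has consequences. For control, section 5.6.3 states: "In the case of progressive disease (PD) in the systemic chemotherapy arm, this treatment will be halted and shifted to 3rd chemotherapy as appropriate". In the HAI arm the systemic line is changed and the pump is no longer used. In the transplant arm the patient stays listed.

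**The concern.** To apply the filter in section 5.6, someone must classify the scan before it is sent. The protocol does not say who, but the scan is done at the local hospital, so the natural reading is that the first classification is made there. That reader did not choose the target lesions and is not blinded. A wrong reading of stable disease is then open to correction at the central meeting. A wrong reading of progression is not, if section 5.6 is the rule in force.

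The endpoints at stake are these:

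- Progression-free survival (secondary in the synopsis, exploratory in Table 1) and liver-progression-free survival (section 8.5.2), because the date of progression is the event.
- Resection rate (Table 1 and section 8.5.2), because section 5 ties resection in the HAI and standard care groups to response on second-line treatment, and a progression call ends that treatment line.
- Response rate (Table 1), but only indirectly. Stable and response scans do reach the centre, so the effect comes through a mistaken progression call that ends treatment before a later response could be seen.

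Overall survival at two years is not read from scans. It could be affected only through a changed treatment or a missed resection.

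**Working it through.** The plan has no figure of its own on this point, so the check is mainly a comparison of sections.

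**Step 1: can both routing rules hold?** Take a scan that shows progression. Under section 5.5 an MDT meeting follows within its schedule and assesses response. Under section 5.6 the scan is not among those submitted. Section 5.6.1 leans towards section 5.5, since it has control and HAI patients evaluated repeatedly, but it does not say that every scan is sent. The rules conflict on exactly this class of scan. This takes the HPB-meeting of section 5.6 and the MDT meeting of sections 5.5 and 5.6.1 to be the same central forum. The protocol gives both the task of judging resectability at the trial hospital and does not describe two separate meetings.

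**Step 2: is a progression call confirmed anywhere else?** Sections 5.6.3 and 5.10 are the places to look. Section 5.6.3 acts on progression without saying who declares it. Section 5.10 sets the criteria without naming a reader. Neither provides for central confirmation.

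**Step 3: does the filter work differently by arm?** Section 5.6 makes no distinction by arm. The resection condition in section 5 is the same for HAI and control.

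**Step 4: what would decide the direction?** Let p be the true resection rate, equal in both arms, and let m_C and m_H be the shares of would-be-resected control and HAI patients lost to a mistaken progression call. The false difference, HAI minus control, is

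D = p(1 − m_H) − p(1 − m_C) = p(m_C − m_H).

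Section 8.1 gives 18 patients in each of these arms. The values of p and m are assumptions; the protocol supplies neither.

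| p | m_C | m_H | D | Patients of 18 | Fisher rejection at two-sided 0.05 |
|---|---|---|---|---|---|
| 0.20 | 0 | 0 | 0 | 0 | 0.02 |
| 0.20 | 0.10 | 0 | 0.02 | 0.36 | 0.02 |
| 0.47 | 0 | 0 | 0 | 0 | 0.03 |
| 0.47 | 0.30 | 0 | 0.141 | 2.54 | 0.09 |
| 0.20 | 0.20 | 0.20 | 0 | 0 | 0.02 |
| 0.47 | 0.20 | 0.20 | 0 | 0 | 0.03 |

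If the loss falls on control alone, D lies between 2 and 14 percentage points over this range. If it is equal, D is zero. If it falls on HAI alone, the sign reverses. The direction therefore depends wholly on m_C − m_H, about which the protocol says nothing. Equal loss would still lower the resection rate in both arms and bring progression dates forward.

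**The case against.** The strongest reply is that section 5.6 describes surgical triage, not endpoint reading. Scans are sent for a resectability decision, resection requires response, and so leaving out progression scans follows naturally. Nothing makes the local call the reading for analysis, and a RECIST review of all scans is not excluded; the statistical analysis plan, not seen here, may deal with it. Part of this stands: one cannot say that local progression calls are never checked, because section 5.5 provides a meeting after each scan. But routing of scans is an operational rule of the protocol, section 5.5 gives that same meeting the task of assessing response, and a later review of images cannot undo a treatment change already made.

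A reader might infer that the bias runs against control, because HAI patients come to the trial hospital for pump fills while control patients are treated locally. The documents do not support this. Pump visits are not scan readings, section 5.5 schedules out-patient outcome appointments for all patients, and the filter and resection condition are common to both arms. The transplant arm does differ, since listing continues after progression. A mistaken call may therefore cost a control patient more than a transplant patient in the resection-versus-transplantation comparison, but this says nothing about HAI against control.

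A reader might also compound an assumed error rate over the six two-monthly scans of the first year: 1 − (1 − p)^6, with p here the error rate per reading, gives 11%, 26% and 47% for 2%, 5% and 10%, or about 2, 5 and 8 of 18 controls. Those rates are invented and the readings are taken as independent. The sum is done for one arm only, so it is not a difference between arms. Section 1.1 gives a median survival of 10 to 12 months from second line, so many patients would not have six scans. And a mistaken call costs a resection only in a patient who would have reached one.

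**Conclusion.** The conflict between sections 5.5 and 5.6 is real and should be resolved. If section 5.6 is followed, progression calls escape the central look that stable and response readings receive, and progression-free survival, liver-progression-free survival and resection rate can be distorted. Response rate is affected only indirectly and the primary endpoint not directly.

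No size can be drawn from the documents, and no direction between HAI and control. The figures in the working show only how the answer depends on assumptions that the protocol does not supply. The conclusion rests on two readings of the text: that scans are classified locally before submission, and that the HPB-meeting and the MDT meeting are the same forum.

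**What to change.** Reconcile sections 5.5 and 5.6 so that every on-study scan in all arms, including those read locally as progression, is submitted to the MDT meeting that section 5.5 already schedules. Record there the RECIST 1.1 status against the baseline target lesions, and state that this is the reading of record for response, progression-free survival and liver-progression-free survival. Record the local call and its date as a separate item, so that disagreement can be reported by arm.

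This concerns endpoint reading only. The sponsor must also reconcile the passages on treatment change after progression (section 5.6.3) and referral for resection (sections 5, 5.6 and 5.6.1) with the chosen routing; no clinical rule is proposed here.

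The cost is a protocol amendment, image transfer of the progression scans and time to read them in an existing meeting. That meeting is itself unblinded and sits at the hospital giving HAI, so the change removes the one-way check but not the lack of blinding.

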5.6.1 Before Treatment Starts

Eligible and consenting patients will be randomized. Patients randomized to systemic chemotherapy will receive chemotherapy at their local hospital. Patients randomized to HIA and systemic chemotherapy will have the pump placement and HAI administration at the department of gastrointestinal surgery/HPB section at OUH/Rikshospitalet. The systemic chemotherapy will be administered at local hospitals. The patients in these two groups will repeatedly be evaluated for liver resection at the MDT-meeting at Rikshospitalet and patients who become resectable will have liver resection/local ablation at Rikshospitalet. Patients randomized to liver transplantation will be evaluated for liver transplantation and receive liver transplantation according to standard procedure at the department of Transplantation Medicine, Rikshospitalet. These patients will receive chemotherapy at their local hospital until time of receiving a liver transplant.

5.6.2 During Treatment

The patients will receive systemic chemotherapy/HAI treatment and regular aout-patient visites as described in flowchart. All patients will have their first visit at 8 weeks post randomization.

5.6.3 Progressive disease or toxicity

In the case of progressive disease (PD) in the systemic chemotherapy arm, this treatment will be halted and shifted to 3rd chemotherapy as appropriate or to best supportive care (BSC). In the case of PD in the HAI-group, systemic chemotherapy will be changed to 3rd line as appropriate and the use of pump is discontinued. In the case of PD in the transplant group, listing is upheld but chemotherapy is changed to 3rd line as appropriate until available organ is available. In the case of toxicity a change in systemic chemotherapy to 3rd line is attempted and if unaltered toxicity, halted.

5.6.4 End of Treatment

The patients will receive systemic chemotherapy/HAI treatment until progressive disease, until resection or until discontinuation due to toxicity or withdrawal of informed consent. Patients receiving liver resection or liver transplantation will have a follow-up for up to 10 years after surgery or until they start palliative chemotherapy. Information on treatment given after liver resection or liver transplantation will be collected. Treatment after relapse of liver resection or liver transplantation will be at the discretion of the treating physician. Patients receiving HAI treatment and having liver resection may have the pump removed at time of liver resection. Patients receiving HAI treatment and not obtaining sufficient response for liver resection will only have the pump removed if the pump is causing symptoms.

5.6.5 After End of Treatment (Follow-up)

Patients having a liver resection or liver transplantation will have follow-up according to Table 6-7. These patients will have follow-up until 10 years after surgery or until they start palliative treatment.

Table 6. Follow-up of resected Excalibur study patients

Follow up Ltx patients	Visits 1 st year (every month)	Visits 2 nd year (every 3 month)	Visits 3 rd -10 th years (every 6 month)
Hb CRP, Hv, Trc, Na, K, Crea	X	X	X
Bilirubin, ASAT, ALAT, ALP, Alb	X	X	X
INR, Cholesterol, glucose, HbA1c	X	X	X
CEA, CA 19-9,	Every 3 months	X	X
TIMP-1, TPA (stop at relapse)	Every 3 months	X	X
5 ml EDTA plasma for later analyses (until relapse)	Every 3 months	X	X
5 ml serum for later analyses (until relapse)	Every 3 months	X	X
Weight	X	X	X

BP	X	X	X
CT thorax/abdomen/pelvis (only in Ltx patients without relapse)	Every 2 months	Every 3 months	Every 6 months
US Liver w/Doppler (only Ltx patients)	Every 3 months		
Coloscopy (only in Ltx patients without relapse)	At 12 months	At 36 months	At 60 months
PET scan (only in patients without lesions on CT)	At 12 months	At 24 months	
EORTC QLQ-C30 and EQ5D	3, 6, 12, months	2 times/year	2 times 3.year

Table 7 Follow-up of Control group, HAI-group and patients not receiving LTx

arm		Outcome	Palliative treatment	Follow Up
3 and 2	Chemo therapy	Surgery	No	10 Years
	FUDR/HAI	PD/Toxicity	yes	Will do "End of treatment visit". OS will be collected.
1	Liver Tx	Transplant	No	10 Years.
		Extra-hepatic disease	yes	Will do "End of treatment visit". OS will be collected.
		Metastasis to lymphnodes	yes	Will do "End of treatment visit". OS will be collected.

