1.7 Rationale for the Study and Purpose

The target population for this study will be patients who based on traditional preoperative criteria have a very dismal prognosis. They will – according to the inclusion criteria – have a large tumour burden and have shown progression on 1st line systemic chemotherapy treatment. Based on previous trials, only 30 % of this patient group will be alive after two years. These patients have today only one treatment modality available: 2nd line systemic chemotherapy. Response can, however, only be expected in a small minority of these patients. As of today, they are not acceptable for inclusion into any of the liver transplant protocols, and hepatic artery infusion (HAI) chemotherapy treatment is not offered in Norway (or any other European country, save the Netherlands, as far as we know).

With such a dismal outcome for these patients, an alternative modality that has the potential to improve survival is highly warranted. While transplantation has such a potential, the access to donor organs will always limit the real-life use of such a treatment and the inclusion of a transplant group in this trial is primarily for proof-of-principle reasons: to benchmark what we have reason to believe is the optimal treatment.

The use of HAI chemotherapy with FUDR has some inherent risks. A laparotomy is necessary to apply the catheter and intra hepatic infusion of FUDR has been reported to cause biliary inflammation and necrosis in a small fraction of the patients. The risk for the latter is however significantly reduced by concomittant steroid infusion. The experiences published from the MSKCC (see further) does however suggest that the drug has few systemic side effects as the first-pass effect in the liver is close to complete, i.e. there is minimal release of active drug into the systemic circulation.

The IMP for use in this protocol does not have a marketing authorization in Europa. The institution that has pioneered the HAI treatment in CRC is Memorial Sloan Kettering Hospital (MSKCC) in New York and the dose is identical to the dose that used in several studies from MSKCC^{14,16} and The Netherlands¹⁷.

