8.5.2 Secondary analyses

- Per-protocol comparison of overall survival at 2 years
- ITT liver-progression-free survival,
- Rates of liver resection in HAI group compared with control group and with transplantation rate for TX group. Standard approximation to binary outcomes with Fisher exact test or chi-square.
- Quality-of-life as measured by EORTC-30

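### Table 7 and section 5.5 disagree on what is collected after progression or a toxicity stop, so the ITT liver-progression-free survival in section 8.5.2 may not be obtainable as named

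*Protocol*

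**What the plan says.** Section 8.5.2 of the protocol lists among the secondary analyses "ITT liver-progression-free survival". It gives no event or censoring rule. The only censoring choice stated for any progression endpoint is in Table 1: PFS with and without censoring at resection or transplantation.

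Table 7 (section 5.6.5) sets follow-up by outcome. For arms 2 and 3 after progression or toxicity, and for arm 1 after extrahepatic disease or lymph-node metastasis, the entry is "Will do 'End of treatment visit'. OS will be collected". The row for arms 2 and 3 does not separate hepatic from extrahepatic progression.

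Section 5.5, under the items for all patients, says: "Control scans are ordered for each 2nd month for the first year following randomization and as long as the patients receive chemotherapy", then "each 3rd month for the second year and each 6th month for the third year". An MDT meeting follows each scan. No stop at progression is given.

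Section 5.6.3 also treats progression at any site alike. In the HAI arm, "systemic chemotherapy will be changed to 3rd line as appropriate and the use of pump is discontinued". In the transplant arm, "In the case of PD in the transplant group, listing is upheld".

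**The concern.** Intention-to-treat liver-progression-free survival needs the liver to be observed until liver progression or death. That includes the time after a first progression in lung or nodes and the time after treatment stops for toxicity. Table 7 read alone provides for survival only from that point.

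The loss need not be equal between arms. Section 1.7 says of FUDR given this way that "there is minimal release of active drug into the systemic circulation". If HAI controls the liver, a larger share of first progressions in that arm will be extrahepatic. Section 5.6.3 then ends pump use, so later liver progression happens off HAI, in exactly the period where Table 7 asks for no liver data.

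An analysis plan can choose a censoring rule, but it cannot recover liver reads that were never collected. The follow-up schedule therefore has to be settled in the protocol.

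**Working it through.** **1. The passages side by side**

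| Situation | Table 7 | Section 5.5 |
|---|---|---|
| Arms 2 and 3, progression at any site | End-of-treatment visit, OS | Scans to year 3 from randomization, and while on chemotherapy |
| Arms 2 and 3, toxicity stop | End-of-treatment visit, OS | Same |
| Arm 1, extrahepatic or nodal disease | End-of-treatment visit, OS | Same |

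Section 5.6.3 moves progressing patients to third-line chemotherapy as appropriate, so the on-chemotherapy scan rule can still apply to them. The year 2 and year 3 scans do not depend on chemotherapy at all. On the other side, Table 6 limits CT after transplantation to patients without relapse. Of resected and transplanted patients section 5.6.5 says: "These patients will have follow-up until 10 years after surgery or until they start palliative treatment". Section 5.6 names only scans showing stable disease or response as going to the central meeting. A site cannot tell which instruction governs.

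**2. Does the counting rule matter?**

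The protocol gives no figure for liver progression, so every rate below is an assumption.

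*Illustration.* Control median time to liver progression is 6 months. Median time to extrahepatic progression is 12 months in both arms. HAI halves the liver hazard while the pump runs, and the hazard returns to the control level afterwards. Median time from extrahepatic progression to death is 10 months. Hazards are ln2/median.

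Share progressing first outside the liver = extrahepatic hazard / (liver + extrahepatic hazard):
- Control: (1/12) / (1/6 + 1/12) = 33%
- HAI: (1/12) / (1/12 + 1/12) = 50%

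Let *l* and *e* be the liver and extrahepatic hazards before progression, A = *l* + *e*, *d* = ln2/10, and B = ln2/6 + *d*. Twelve-month liver-PFS is:
- Full liver follow-up: exp(−12A) + *e*[exp(−12A) − exp(−12B)]/(B − A). Control: 0.125 + 0.081 = 21%. HAI: 0.250 + 0.118 = 37%.
- Censored at extrahepatic progression: exp(−12*l*). Control 25%, HAI 50%.
- Death only afterwards: exp(−12A) + *e*[exp(−12*d*) − exp(−12A)]/(A − *d*). Control: 0.125 + 0.172 = 30%. HAI: 0.250 + 0.232 = 48%.

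Cox hazard ratios to 24 months, simulated with 6,000 patients per arm, were 0.61 with full follow-up, 0.48 censored (0.50 by construction) and 0.62 with death only. With no HAI effect the hazard ratio stayed near 1.0.

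*Wider grid.* A separate simulation used 40,000 patients per arm over 24 months. Control median to liver progression was 6 months. Control median to extrahepatic progression was 8, 15 or 30 months, the HAI liver hazard ratio 0.4 or 0.6, and the HAI extrahepatic hazard ratio 0.7 or 1.0. Frailty variance was 0 or 1, the liver effect was kept or lost after the pump stops, and median time from first progression to death was 10 months. That is 3 × 2 × 2 × 2 × 2 = 48 scenarios. The reference is liver progression or death with liver imaging continued.

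| Handling of extrahepatic-first progression | Lower HR than reference (favours HAI) | Equal | Higher HR (against HAI) | Range of difference in HR |
|---|---|---|---|---|
| Censor there | 48 | 0 | 0 | −0.257 to −0.008 |
| Follow for death only | 11 | 1 | 36 | −0.047 to +0.129 |
| Count it as the event | 7 | 0 | 41 | −0.041 to +0.157 |

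Example (8 months, liver hazard ratio 0.4, extrahepatic hazard ratio 1.0, no frailty, effect kept): reference 0.50, censored 0.40, death only 0.61, any progression 0.66. With the effect lost: 0.62, 0.40, 0.62 and 0.66.

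**The case against.** A reader might infer that Table 7 stops all imaging, so that liver progression after extrahepatic progression is never seen. The documents do not say this. Table 7 names no imaging but does not end it, and section 5.5 keeps all patients on a scan calendar to year 3. In arm 1, section 5.6.3 keeps the patient listed at progression, with chemotherapy continuing. What stands is a conflict between two instructions, not a fixed stop.

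A reader might also infer that the liver endpoint overstates HAI. That needs censoring at extrahepatic progression, which the protocol never states. Deaths are collected, and death is ordinarily an event in progression-free survival. With death kept as the event, the illustration gives 0.62 against 0.61, and only the survival levels rise, in both arms.

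Three further objections have weight:
- All rates are assumed, neither simulation describes resection, and the gap can be as small as 0.01.
- Section 8.1 plans 18 patients in each of the HAI and control groups. Even with 36 events, the standard error of the log hazard ratio is about √(4/36) = 0.33. A shift from 0.61 to 0.50 is ln(0.61/0.50) = 0.20, or about 0.6 standard errors.
- Liver-PFS is one line in section 8.5.2 and is absent from Table 1, where PFS is exploratory.

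These limit the importance of the point. They do not remove the conflict, and a later analysis plan cannot supply missing liver reads.

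**Conclusion.** The point holds as an inconsistency with a consequence for one secondary analysis. Table 7 and section 5.5 must be reconciled. If Table 7 governs, liver-progression-free survival cannot be obtained on an intention-to-treat basis for patients who first progress outside the liver or who stop for toxicity. If the section 5.5 calendar governs, the loss does not arise while that calendar runs.

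The direction of bias is not fixed by the protocol. Censoring at extrahepatic progression would favour HAI in every scenario tested, by about 0.01 to 0.26 on the hazard-ratio scale. The other two handlings are mostly neutral or against HAI, with small exceptions when the liver effect is lost after the pump stops. These sizes rest wholly on assumed rates. The primary overall survival analysis is unaffected. Severity is modest.

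**What to change.** In Table 7, state that neither extrahepatic progression nor a toxicity stop ends collection of liver-progression data. Liver reads from scans already on the section 5.5 calendar, including those taken during third-line chemotherapy, are collected until liver progression, death or the end of that calendar. This adds no scan beyond section 5.5 and changes no treatment.

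In section 8.5.2, state that patients are not treated as non-informatively censored at extrahepatic progression. Where no later liver scan exists, report the cumulative incidence of liver progression with extrahepatic progression and death as competing events, and do not call that result ITT liver-PFS.

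The cost is wording in two places, some collection of scans from local hospitals, and possibly a less favourable liver estimate for HAI than censoring would give.
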